11. MEASUREMENT OF EFFECT

11.1 Antitumor Effect– Solid Tumors

Response and progression will be evaluated in this study using the new international criteria proposed by the Response Evaluation Criteria in Solid Tumors (RECIST) guideline (version 1.1) [Eur J Ca 45:228-247, 2009]. Changes in the largest diameter (unidimensional measurement) of the tumor lesions and the shortest diameter in the case of malignant lymph nodes are used in the RECIST criteria.

11.1.1 Definitions

Evaluable for Target Disease response. Only those participants who have measurable disease present at baseline, have received at least one cycle of therapy, and have had their disease re-evaluated will be considered evaluable for target disease response. These participants will have their response classified according to the definitions stated below. (Note: Participants who exhibit objective disease progression prior to the end of cycle 1 will also be considered evaluable.)

CONFIDENTIAL

This document is confidential. Do not disclose or use except as authorized.

Evaluable Non-Target Disease Response. Participants who have lesions present at baseline that are evaluable but do not meet the definitions of measurable disease, have received at least one cycle of therapy, and have had their disease re-evaluated will be considered evaluable for non-target disease. The response assessment is based on the presence, absence, or unequivocal progression of the lesions.

11.1.2 Disease Parameters

Measurable disease. Measurable lesions are defined as those that can be accurately measured in at least one dimension (longest diameter to be recorded) as ≥ 20 mm by chest x-ray or ≥ 10 mm with CT scan, MRI, or calipers by clinical exam. All tumor measurements must be recorded in millimeters (or decimal fractions of centimeters).

Note: Tumor lesions that are situated in an irradiated area are not considered measurable.

Malignant lymph nodes. To be considered pathologically enlarged and measurable, a lymph node must be ≥ 15 mm in short axis when assessed by CT scan (CT scan slice thickness recommended to be no greater than 5 mm). At baseline and in follow-up, only the short axis will be measured and followed.

Non-measurable disease. All other lesions (or sites of disease), including small lesions (longest diameter <10 mm or pathological lymph nodes with ≥ 10 to <15 mm short axis), are considered non-measurable disease. Bone lesions, leptomeningeal disease, ascites, pleural/pericardial effusions, lymphangitis cutis/pulmonitis, inflammatory breast disease, abdominal masses (not followed by CT or MRI), and cystic lesions are all considered non-measurable.

Note: Cystic lesions that meet the criteria for radiographically defined simple cysts should not be considered as malignant lesions (neither measurable nor non-measurable) since they are, by definition, simple cysts.

‘Cystic lesions’ thought to represent cystic metastases can be considered as measurable lesions, if they meet the definition of measurability described above. However, if non-cystic lesions are present in the same participant, these are preferred for selection as target lesions.

Target lesions. All measurable lesions up to a maximum of 2 lesions per organ and 5 lesions in total, representative of all involved organs, should be identified as **target lesions** and recorded and measured at baseline. Target lesions should be selected on the basis of their size (lesions with the longest diameter), be representative of all involved organs, but in addition should be those that lend themselves to reproducible repeated measurements. It may be the case that, on occasion, the largest lesion does not lend itself to reproducible measurement in which circumstance the next largest lesion which can be measured reproducibly should be selected. A sum of the diameters (longest for non-nodal lesions, short axis for nodal lesions) for all target lesions will be calculated and reported as the baseline sum diameters. If lymph nodes are to be included in the sum, then only the short axis is added into the sum. The baseline sum diameters will be used as reference to further characterize any objective tumor regression in the measurable dimension of the disease.

CONFIDENTIAL

This document is confidential. Do not disclose or use except as authorized.

Non-target lesions. All other lesions (or sites of disease) including any measurable lesions over and above the 5 target lesions should be identified as **non-target lesions** and should also be recorded at baseline. Measurements of these lesions are not required, but the presence, absence, or in rare cases unequivocal progression of each should be noted throughout follow up.

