5.4.2 Radiation treatment

5.4.2.1 Prioritizing lesions for irradiation

In addition to providing palliative benefit, this study attempts to use radiation to engender a systemic immune response in the context of PD-1 inhibition. Therefore, the choice of site or sites irradiated will be based on a combination of safety, palliative benefit and, if feasible, correlative studies will in parallel evaluate whether there is an association between abscopal responses and personalized stratification based on hypothetical T-cell trafficking[61]. Prior to radiation simulation, initial staging scans will be analyzed in detail. Lesions will be prioritized for treatment as follows (in order of priority): 1) Lesions must be safe to irradiate at the dose prescribed by the protocol as deemed by the treating radiation oncologist and able to meet standardly accepted radiation dose constraints and as specified below; 2) Lesions must be irradiated for potential palliative benefit as determined by the treating physicians; 3) Lesions that have not responded or progressed on prior immune checkpoint blockade. 4) The largest lesion that meets the criteria states above determined using bidirectional measurements. Based on this algorithm, the top rated lesion will receive 8 Gy in each of 3-5 fractions. In cohort B, the goal is to irradiate a significant percentage, if not all of the total visible tumor burden.

In parallel, we will investigate the feasibility of ranking all metastatic lesions in terms of the theoretic potential of these lesions to stimulate an immune response at a distant, unirradiated metastatic site as described in more detail in the correlative studies section.

5.4.2.2 Treatment simulation: The treatment planning process will include CT based simulation with 1.25- 2.5-mm cuts to cover the area(s) of interest.

CONFIDENTIAL

This document is confidential. Do not disclose or use except as authorized.

5.4.2.3 Contours: Several tumor contours will be defined by the physician:

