11.1.4 Response Criteria

11.1.4.1 Evaluation of Target Lesions (Note: irradiated target lesions are excluded from overall response determination)

Complete Response (CR): Disappearance of all target lesions. Any pathological lymph nodes (whether target or non-target) must have reduction in short axis to <10 mm.

Partial Response (PR): At least a 30% decrease in the sum of the diameters of target lesions, taking as reference the baseline sum diameters.

Progressive Disease (PD): At least a 20% increase in the sum of the diameters of target lesions, taking as reference the smallest sum on study (this includes the baseline sum if that is the smallest on study). In addition to the relative increase of 20%, the sum must also demonstrate an absolute increase of at least 5 mm. (Note: the appearance of one or more new lesions is also considered progressions).

Stable Disease (SD): Neither sufficient shrinkage to qualify for PR nor sufficient increase to qualify for PD, taking as reference the smallest sum diameters while on study.

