11.1.4.2 Evaluation of Non-Target Lesions

Complete Response (CR): Disappearance of all non-target lesions and normalization of tumor marker level. All lymph nodes must be non-pathological in size (<10 mm short axis).

Note: If tumor markers are initially above the upper normal limit, they must normalize for a patient to be considered in complete clinical response.

Non-CR/Non-PD: Persistence of one or more non-target lesion(s) and/or maintenance of tumor marker level above the normal limits.

Progressive Disease (PD): Appearance of one or more new lesions and/or *unequivocal progression* of existing non-target lesions. *Unequivocal progression* should not normally trump

target lesion status. It must be representative of overall disease status change, not a single lesion increase.

Although a clear progression of “non-target” lesions only is exceptional, the opinion of the treating physician should prevail in such circumstances, and the progression status should be confirmed at a later time by the review panel (or Principal Investigator).

The finding of a new lesion should be unequivocal (i.e. not due to difference in scanning technique, imaging modality, or findings thought to represent something other than tumor (for example, some ‘new’ bone lesions may be simply healing or flare of pre-existing lesions). However, a lesion identified on a follow-up scan in an anatomical location that was not scanned at baseline is considered new and will indicate PD. If a new lesion is equivocal (because of small size etc.), follow-up evaluation will clarify if it truly represents new disease and if PD is confirmed, progression should be declared using the date of the initial scan on which the lesion was discovered.

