11.2.8 Abscopal response rate

Abscopal response is defined as described previously [62] to be a decrease in the longest diameter of at least 30% in any measurable (>1cm) non-irradiated lesion from baseline. A complete abscopal response is defined as the complete disappearance of a measurable non-irradiated lesion and a partial abscopal response was defined as at least a 3-% decrease in the longest diameter. Progressive disease in this context is defined as at least a 20% increase in the longest diameter of the best measurable non-irradiated lesion, whereas stable disease was defined as insufficient shrinkage or growth to qualify for a partial abscopal response or complete abscopal response or progressive disease.

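### Target lesions are chosen by size without regard to the radiation plan, so where a RECIST cap binds, measurable unirradiated lesions can be left as non-target disease that need not be measured

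*Combined protocol and SAP*

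**What the plan says.** **Target selection (11.1.2).** The cap is "All measurable lesions up to a maximum of 2 lesions per organ and 5 lesions in total", and within it "Target lesions should be selected on the basis of their size (lesions with the longest diameter), be representative of all involved organs". Reproducible measurement is a further consideration. Everything else is non-target, and for non-target lesions the section says "Measurements of these lesions are not required".

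**Choice of lesions to irradiate (5.4.2.1).** Lesions are ranked from the initial staging scans by safety, then palliative benefit, then lack of response or progression on earlier checkpoint blockade, and lastly size: "The largest lesion that meets the criteria states above determined using bidirectional measurements". Cohort A irradiates one lesion (5.1). For Cohort B, "the goal is to irradiate a significant percentage, if not all of the total visible tumor burden".

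**Exclusion (11.1.4.1).** A note says that "irradiated target lesions are excluded from overall response determination". A separate note in 11.1.2 treats lesions in an irradiated area as not measurable, without saying whether fields planned on study are included.

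**Non-target progression (11.1.4.2).** New lesions and unequivocal progression of non-target disease count as PD. Of unequivocal progression the section says: "It must be representative of overall disease status change, not a single lesion increase".

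**Abscopal response (11.2.8).** It is defined as "a decrease in the longest diameter of at least 30% in any measurable (>1cm) non-irradiated lesion from baseline", so it is not restricted to target lesions.

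**The concern.** Target selection and radiation planning start from the same baseline disease, and both use size, although for radiation it comes last. Nothing in the plan makes one list take account of the other. If a lesion fills a target slot and is then irradiated, it leaves the overall response assessment and its slot stays empty. An unirradiated lesion that was kept out by the cap remains non-target.

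The primary endpoint is the 3-month PFS rate by RECIST 1.1, and overall and abscopal response are secondary. For a lesion left outside the measured sum, a 20% increase (with at least 5 mm) does not trigger target PD, and a 30% decrease does not count towards PR. Progression then depends on new lesions or on a judgment of unequivocal progression, in an open-label study with no control arm. A progression missed in this way can only raise the observed PFS rate. For abscopal response, the endpoint needs diameters that the measurement section does not ask sites to record.

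**Working it through.** **1. The plan's own figure.** Section 13.1 gives 6 patients in stage 1, continuation with at least 2 progression-free, success with at least 10 of 19, rates of 35% and 65%, 90% power and one-sided level 0.08. The exact probability of success is the sum over x = 2 to 6 of P(X1 = x) × P(X2 ≥ 10 − x), with X1 ~ Bin(6, p) and X2 ~ Bin(13, p).

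- p = 0.35: 0.0152 + 0.0305 + 0.0270 + 0.0102 + 0.0013 = 0.0842.
- p = 0.65: 0.0681 + 0.2050 + 0.3129 + 0.2406 + 0.0752 = 0.9018.

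The stated level and power reproduce. They are not in dispute.

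**2. When a measured lesion is lost.** I applied the 11.1.2 rule (largest first, 2 per organ, 5 in total) and removed the irradiated lesions. I then counted the unirradiated targets left, and compared that with filling the slots from unirradiated lesions only. The layouts are assumptions, and so is the premise that the largest lesions are the ones irradiated.

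| Measurable lesions | Irradiated | Unirradiated targets, current rule | Slots filled from unirradiated lesions |
|---|---|---|---|
| 2+1 in two organs | 1 | 2 | 2 |
| 2+2+1 in three organs | 1 | 4 | 4 |
| 2+2+1 in three organs | 3 | 2 | 2 |
| 3 in one organ | 1 | 1 | 2 |
| 3 in one organ | 2 | 0 | 1 |
| 6 in one organ | 1 | 1 | 2 |
| 6 in one organ | 2 to 4 | 0 | 2 |
| 4+2 in two organs | 2 | 2 | 4 |
| 3+3+2 in three organs | 1 | 4 | 5 |
| 3+3+2 in three organs | 4 | 2 | 4 |

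The first three rows lie within the caps and lose nothing. In the others a cap binds. With one lesion irradiated, as in Cohort A, the loss is at most one target. With two or more irradiated in an organ that holds three or more, that organ can be left with no measured unirradiated lesion.

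**3. One patient followed through.** Take four lung lesions of 40, 30, 25 and 20 mm (assumed). The targets are the 40 and 30 mm lesions.

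- Cohort B, with the 40, 30 and 25 mm lesions irradiated: no target remains for overall response, and the 20 mm lesion is non-target. Growth to 28 mm is 8/20 = +40% and +8 mm, which meets both numerical PD conditions but is not target PD. Shrinkage to 13 mm is −7/20 = −35%, which would be PR for a sole target but is Non-CR/Non-PD for a non-target lesion.
- Cohort A, with the 40 mm lesion irradiated: the 30 mm lesion remains a measured unirradiated target. Reordering the selection would add the 25 mm lesion as a second.

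**4. Illustration for the decision rule.** Let d be the share of true 3-month failures recorded as progression-free. At a true rate of 35% the observed rate is 0.35 + 0.65d. The values of d are assumed.

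| d | Observed rate | Probability of success |
|---|---|---|
| 0 | 0.3500 | 0.084 |
| 5% | 0.3825 | 0.141 |
| 10% | 0.4150 | 0.217 |

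**5. Abscopal response.** Section 11.2.8 needs baseline and follow-up diameters of any non-irradiated lesion over 1 cm. Section 11.1.2 does not require them for non-target lesions. The endpoint definition and the measurement rule do not match.

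**The case against.** A reader might infer that both lists are drawn up largest-first, so that they coincide and unirradiated disease generally goes unmeasured. The documents do not support that. Size is the fourth radiation criterion, target choice also weighs organ representation and reproducibility, and no overlap figure is given. All measurable lesions are targets until a cap binds. The Cohort B example above shows a large effect by construction, and Cohort B opens only if 0 or 1 of the first 6 Cohort A patients is progression-free.

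A second tempting inference is that progression in these lesions is ignored for PFS. It is not. New lesions and unequivocal non-target progression give PD, and where only non-target disease progresses the treating physician's opinion prevails, with later confirmation. In the example the 20 mm lesion is the only unirradiated disease, so its growth could be judged representative of overall status. What is lost is the numerical trigger.

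Third, the note that lesions in an irradiated area are not measurable could be read to bar planned-field lesions from being targets, which would remove the problem. But 11.1.4.1 presupposes irradiated targets, so the two notes are unreconciled. Nor does 11.1.4.1 say that its exclusion governs PD for PFS. If irradiated targets stayed in the sum for PD, the surplus unirradiated lesion would still be outside it.

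Fourth, non-target measurements are not forbidden, and 9.3.3 plans to rank lesions and study which distant lesions respond. Scans could be re-read later. The abscopal gap is therefore a missing requirement to record; it does not show that data will be lost.

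These points limit how often the problem arises and how large it is. None supplies a rule for reserving or replacing target slots.

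**Conclusion.** The point holds as a conditional one. Where the 2-per-organ or 5-in-total cap binds and target lesions are irradiated, measurable unirradiated lesions can be left without the quantitative PD and PR criteria and without required diameters. Cohort A loses at most one target per patient through the initial plan. Cohort B can lose all measured unirradiated disease in an organ. Patients within the caps lose nothing.

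The direction of any effect on the 3-month PFS rate is upward. Its size cannot be derived, because the documents give neither lesion counts per patient nor a rate of missed progression. The rise from 0.084 to 0.141 or 0.217 rests entirely on the assumed 5% and 10%. It should not be read as the trial's actual type I error, and the stated design figures stand. The point concerns baseline target selection and the initial radiation plan, not radiation in later cycles. Should-fix.

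**What to change.** In 11.1.2, state that target lesions are chosen after the initial radiation plan is set and before the first fraction, with the slots (2 per organ, 5 in total) filled first from measurable lesions not planned for irradiation. In addition:

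- Record and measure irradiated lesions separately, for local response under 11.2.7.
- Require diameters at baseline and at each scan for every measurable unirradiated lesion used for abscopal response.
- Reconcile the 11.1.2 note on irradiated areas with 11.1.4.1, and state whether the 11.1.4.1 exclusion also applies to PD for PFS.
- List the patients who have no unirradiated measurable lesion at baseline. Reordering the selection cannot help them, and Cohort B's stated goal makes such patients possible.

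The cost is a short amendment to section 11, a case report form change and some added diameter measurements. Scans, readers and treatment stay the same. The downside is that the target sum may rest on smaller lesions, with somewhat more measurement error.

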11.1.3 Methods for Evaluation of Measurable Disease

All measurements should be taken and recorded in metric notation using a ruler, calipers, or a digital measurement tool. All baseline evaluations should be performed as closely as possible to the beginning of treatment and never more than 4 weeks before the beginning of the treatment.

The same method of assessment and the same technique should be used to characterize each identified and reported lesion at baseline and during follow-up. Imaging-based evaluation is preferred to evaluation by clinical examination unless the lesion(s) being followed cannot be imaged but are assessable by clinical exam.

Clinical lesions. Clinical lesions will only be considered measurable when they are superficial (e.g., skin nodules and palpable lymph nodes) and ≥ 10 mm in diameter as assessed using calipers (e.g., skin nodules). In the case of skin lesions, documentation by color photography, including a ruler to estimate the size of the lesion, is recommended.

Chest x-ray. Lesions on chest x-ray are acceptable as measurable lesions when they are clearly defined and surrounded by aerated lung; however, CT is preferable.

Conventional CT and MRI. This guideline has defined measurability of lesions on CT scan based on the assumption that CT thickness is 5mm or less. If CT scans have slice thickness greater than 5 mm, the minimum size of a measurable lesion should be twice the slice thickness. MRI is also acceptable in certain situations (e.g. for body scans).

Use of MRI remains a complex issue. MRI has excellent contrast, spatial, and temporal resolution; however, there are many image acquisition variables involved in MRI, which greatly impact image quality, lesion conspicuity, and measurement. Furthermore, the availability of MRI is variable globally. As with CT, if an MRI is performed, the technical specifications of the scanning sequences used should be optimized for the evaluation of the type and site of disease. Furthermore, as with CT, the modality used at follow-up should be the same as was used at baseline and the lesions should be measured/assessed on the same pulse sequence. It is beyond the scope of the RECIST guidelines to prescribe specific MRI pulse sequence parameters for all scanners, body parts, and diseases. Ideally, the same type of scanner should be used and the image acquisition protocol should be followed as closely as possible to prior scans. Body scans should be performed with breath-hold scanning techniques, if possible.

FDG-PET. While FDG-PET response assessments need additional study, it is sometimes reasonable to incorporate the use of FDG-PET scanning to complement CT scanning in assessment of progression (particularly possible 'new' disease). New lesions on the basis of FDG-PET imaging can be identified according to the following algorithm:

CONFIDENTIAL

This document is confidential. Do not disclose or use except as authorized.

- (a) Negative FDG-PET at baseline, with a positive FDG-PET at follow-up is a sign of PD based on a new lesion.
- (b) No FDG-PET at baseline and a positive FDG-PET at follow-up: If the positive FDG-PET at follow-up corresponds to a new site of disease confirmed by CT, this is PD. If the positive FDG-PET at follow-up is not confirmed as a new site of disease on CT, additional follow-up CT scans are needed to determine if there is truly progression occurring at that site (if so, the date of PD will be the date of the initial abnormal FDG-PET scan). If the positive FDG-PET at follow-up corresponds to a pre-existing site of disease on CT that is not progressing on the basis of the anatomic images, this is not PD.
- (c) FDG-PET may be used to upgrade a response to a CR in a manner similar to a biopsy in cases where a residual radiographic abnormality is thought to represent fibrosis or scarring. The use of FDG-PET in this circumstance should be prospectively described in the protocol and supported by disease-specific medical literature for the indication. However, it must be acknowledged that both approaches may lead to false positive CR due to limitations of FDG-PET and biopsy resolution/sensitivity.

Note: A ‘positive’ FDG-PET scan lesion means one which is FDG avid with an uptake greater than twice that of the surrounding tissue on the attenuation corrected image.

PET-CT. At present, the low dose or attenuation correction CT portion of a combined PET-CT is not always of optimal diagnostic CT quality for use with RECIST measurements. However, if the site can document that the CT performed as part of a PET-CT is of identical diagnostic quality to a diagnostic CT (with IV and oral contrast), then the CT portion of the PET-CT can be used for RECIST measurements and can be used interchangeably with conventional CT in accurately measuring cancer lesions over time. Note, however, that the PET portion of the CT introduces additional data which may bias an investigator if it is not routinely or serially performed.

Ultrasound. Ultrasound is not useful in assessment of lesion size and should not be used as a method of measurement. Ultrasound examinations cannot be reproduced in their entirety for independent review at a later date and, because they are operator dependent, it cannot be guaranteed that the same technique and measurements will be taken from one assessment to the next. If new lesions are identified by ultrasound in the course of the study, confirmation by CT or MRI is advised. If there is concern about radiation exposure from CT, MRI may be used instead of CT in selected instances.

Endoscopy, Laparoscopy. The utilization of these techniques for objective tumor evaluation is not advised. However, such techniques may be useful to confirm complete pathological response when biopsies are obtained or to determine relapse in trials where recurrence following complete response (CR) or surgical resection is an endpoint.

Tumor markers. Tumor markers alone cannot be used to assess response. If markers are initially above the upper normal limit, they must normalize for a participant to be considered in complete clinical response. Specific guidelines for both CA-125 response (in recurrent ovarian cancer) and PSA response (in recurrent prostate cancer) have been published [JNCI 96:487-488, 2004; J Clin Oncol 17, 3461-3467, 1999; J Clin Oncol 26:1148-1159, 2008]. In addition, the Gynecologic

Cancer Intergroup has developed CA-125 progression criteria which are to be integrated with objective tumor assessment for use in first-line trials in ovarian cancer [JNCI 92:1534-1535, 2000].

Cytology, Histology. These techniques can be used to differentiate between partial responses (PR) and complete responses (CR) in rare cases (e.g., residual lesions in tumor types, such as germ cell tumors, where known residual benign tumors can remain).

The cytological confirmation of the neoplastic origin of any effusion that appears or worsens during treatment when the measurable tumor has met criteria for response or stable disease is mandatory to differentiate between response or stable disease (an effusion may be a side effect of the treatment) and progressive disease.

